I agree to comply with the International Conference on Harmonization Tripartite Guideline on Good Clinical Practice, all applicable national regulations as well as the requirements of the appropriate Institutional Review Board/Independent Ethics Committee and any other institutional requirements.

I agree to ensure that the confidential information contained in this document will not be used for any purpose other than the evaluation or conduct of the clinical investigation without the prior written consent of the study sponsor.

Signature

Date (DD Month YYYY)

Investigator

Investigator's Institution

SYNOPSIS

Protocol code.	SAIL
Protocol version (Date)	Version 3.1, dated 13.01.2017
Detailed title	Evaluation of Ara-C and Idarubicin in Combination with the Selective Inhibitor of Nuclear Export (SINE) Selinexor (KPT-330) in Patients with relapsed or refractory AML
EudraCT no.	2014-000526-37
LKP according to §4 Abs. 25 and §40 Abs. 1 Nr. 5 AMG	[name]. [name], Hannover
Sponsor	GSO Global Clinical Research B.V. EBC Amsterdam [name] The Netherlands
Study design	
Multi center, open-label, non-randomized Phase 2 trial.
 
Patients with relapsed/refractory Acute Myeloid Leukemia (AML) will receive standard chemotherapy cytosine arabinose (Ara-C) 100mg/m² days 1-7 and Idarubicin 10 mg/m² days 1, 3, 5 every 4 weeks (max. 2 cycles) and Selinexor as a flat dose of 60 mg twice weekly during weeks 1-3 of a 4-week cycle starting on Day 2 of week 1 (total of 6 doses per induction cycle).
 
If a bone marrow CR or CRI was achieved the patient will be recommended for stem cell transplantation, which represents the end of study treatment.
 
If a partial remission was achieved an additional induction cycle will be initiated.
 
Patients achieving CR or CRI, who are not eligible for SCT will receive consolidation therapy with AraC (3 cycles) in parallel to maintenance with Selinexor until relapse.
 
Patients with >50% blast reduction after 2 cycles will continue maintenance with Selinexor until PD.
 
Patients will be evaluated for disease status at the end of each 4-weeks induction cycle and approximately every 3 months after allogeneic SCT or CR (or CRI) has been achieved until relapse or death, whichever is first.

Duration of study	
The planned number of 40 patients was reached.
 
End of enrolment period: June 2016.
 
End of study is defined as 2 years after registration of last patient

Total number of sites	6-8

Study population	Patients with relapsed/refractory Acute Myeloid Leukemia (AML) according to the inclusion and exclusion criteria will be enrolled in this study trial.
Objectives	
Primary objective	
 To determine the efficacy of Selinexor in combination with standard chemotherapy in patients with relapsed/ refractory AML by determination of rate of complete remission (CR) or morphologic complete remission with incomplete blood count recovery (CRi), as defined by the recommendations on diagnosis and management of AML in adults from an international expert panel, on behalf of the European LeukemiaNet⁽¹⁾
Secondary objectives	
 To determine the efficacy of Selinexor in combination with standard chemotherapy in patients with relapsed/ refractory AML by 
 Rate of partial remissions Percentage of patients being transplanted after induction therapy Early death rate Overall survival (OS) Event-free survival To evaluate overall safety and tolerability of Selinexor characterized by type, frequency, severity (graded using the National Cancer Institute Common Terminology Criteria for Adverse Events [NCI CTCAE] Version 4.03), timing and relatedness of adverse events (AEs) and laboratory abnormalities observed during the treatment within this study.
Exploratory objectives	To identify the Pharmacokinetics and Pharmacodynamics of Selinexor in patients with relapsed/refractory AML
Planned sample size	A sample size of 40 patients is planned and all patients receive standard chemotherapy with Selinexor. If a CR is achieved patients are intended to receive stem cell transplantation.
Inclusion criteria	
To be eligible for this trial, patients must meet the following criteria:
 
 Cytological or histological diagnosis of AML with the exception of promyelocytic leukemia (AML M3) Patients must have relapsed/refractory disease (relapse after stem cell transplantation is permitted) as defined as: patients with <PR after first cycle of induction chemotherapy, or 
 patients with <CR(i) after second cycle of induction chemotherapy, or patients who relapse after conventional chemotherapy or patients who have undergone a single stem cell transplantation and who have relapse of their AML.

	
 3. Men and women aged ≥ 18 years and eligible for standard dose of chemotherapy (7+3); 4. A period of at least 3 weeks needs to have elapsed since last treatment (with the exception of hydroxyurea) before participating in this study. Hydroxyurea induction therapy to reduce peripheral blast counts is permitted prior to initiation of treatment on protocol. Treatment may begin in <3 weeks from last treatment if deemed in the best interest of the patient after discussion with the PI of the study; 5. ECOG performance status ≤ 2 6. Serum biochemical values with the following limits unless considered due to leukemia: creatinine ≤ 2 mg/dl; total bilirubin ≤ 2x ULN, unless increase is due to hemolysis or congenital disorder; transaminases (SGPT or SGOT) ≤ 2.5x ULN. 7. Ability to swallow and retain oral medication 8. Ability to understand and provide signed informed consent; 9. Cardiac ejection fraction must be $>/=50\%$ (by echocardiography). 10. Willingness and ability to comply with scheduled visits, treatment plans, laboratory tests, and other study procedures.
Exclusion criteria	
Patients with any of the following will not be eligible for participation:
 
 1. Treatment with any investigational agent within four weeks. 2. Cumulative anthracycline dose (daunorubicin or equivalent) >360 mg/m² 3. HIV infection 4. Presence of any medical or psychiatric condition which may limit full compliance with the study, including but not limited to: 5. Presence of CNS leukemia 6. Unresolved toxicity from previous anti-cancer therapy or incomplete recovery from surgery. 7. For patients after SCT as part of prior treatment: 
 a. Necessity of immunosuppressive drugs b. GvHD $>$ grade 1 8. Any of the following within the 12 months prior to study drug administration: myocardial infarction, severe/unstable angina, coronary/peripheral artery bypass graft, symptomatic congestive heart failure, cerebrovascular accident or transient ischemic attack, pulmonary embolism, deep vein thrombosis, or other thromboembolic event. 9. Ongoing cardiac dysrhythmias of NCI CTCAE Grade ≥ 2. 10. Other severe acute or chronic medical or psychiatric condition, or laboratory abnormality that may increase the risk associated with study participation or study drug administration, or may interfere with the interpretation of study results, and in the judgment of the investigator would make the patient inappropriate for entry into this study. 11. Clinically significant bleeding within 1 month

Treatment scheme	
All enrolled patients may participate in an optional baseline translational research study. Patients will receive single dose of Selinexor (60 mg) after registration and before first induction cycle. Bone marrow aspirate samples will be collected pre-dose and 24 hour post-dose.
 
All enrolled patients will be treated with Ara-C at a dose of 100 mg/m² continuous infusion (day 1-7) and idarubicin at a dose of 10 mg/m² iv (day 1,3,5) every 4 weeks and Selinexor. If a second cycles is applied idarubicin is only given on day 1 and 3).
 
Selinexor will be administered at a dose of 60 mg twice weekly orally during weeks 1-3 of a 4-week cycle (day 2,4,9,11,16,18) (total of 6 doses per induction cycle).
 
If a CR was achieved the patient will be recommended for stem cell transplantation and will have his/her end of treatment and will be followed for event-free and overall survival.
 
If patient has achieved a PR an additional cycle (4 weeks) will be initiated. If a CR was achieved the patient will be recommended for stem cell transplantation and will be followed for event-free and overall survival.
 
In patients achieving CR or CRi after 1 or 2 4-week cycles who are not eligible or do not undergo additional stem cell transplantation, but, in the opinion of the investigator, are benefiting from Selinexor, then oral Selinexor dosed twice weekly may be continued parallel to consolidation therapy with Ara-C until relapse or toxicity develops. The dose of Ara-C is 3 g/m² IV for 2h every 12 hours at 3 consecutive days for patients with good performance status and younger than 60 years (in total 6 doses). If patients are older than 60 years the dose is 1 g/m² IV for 2h every 12 hours at 3 consecutive days. Consolidation with AraC will consist of 3 4-week cycles. During consolidation Selinexor dosing (60 mg) will start on day 2 and continue twice weekly in weeks 1-3 of a 4-week cycle (total of 6 doses per cycle). Selinexor twice weekly (with ~48 hours between two consecutive doses) in weeks 1-3 of a 4-week cycle at a dose of 60 mg (total of 6 doses per 4-week cycle) may continue until relapse or for maximally 1 year of treatment.
 
Patients achieving a > 50% blast reduction after the end of 2 induction cycles, not candidates for SCT, and in the opinion of the investigator, are benefiting from Selinexor, oral Selinexor dosed twice weekly may be continued until PD or for maximally 1 year of treatment. Drug administration will occur twice weekly with ~48 hours between two consecutive doses at a dose of 60 mg. One cycle is 4 weeks with 6 doses of Selinexor during weeks 1-3. (e.g.

------------------	---

	
on Monday and Wednesday or on Tuesday and Thursday or on Wednesday and Friday).
 
Treatment will continue until progression of disease (PD) or unacceptable toxicity, withdrawal of consent by the patients, or non-compliance by the patient with protocol requirements.
 
Patients for whom none of the above mentioned is achieved after 2 4-week induction cycles will have their end of treatment and will be followed for overall survival.

Primary Endpoint	Percentage of patients achieving a complete response (CR) or CRI (complete remission without normalization of peripheral blood counts)
Secondary Endpoints	
 • Partial response rate • Percentage of patients undergoing subsequent allogeneic stem cell transplant • Early death rate • Overall survival (OS) • Event-free survival (Events are defined as Death, not achieving a CR or CRI, Relapse after CR or CRI) • Toxicity (acc. to NCI CTC AE v4.03)
Exploratory Endpoints (Optional Studies)	
 • Limited pharmacokinetics to measure plasma concentration of Selinexor • Selinexor-induced changes in mRNA levels of XPO1 and tumor suppressor markers • Selinexor-induced changes in plasma cytokine levels • Selinexor-induced changes in gene expression profiling of leukemic blasts isolated from patients • Expansion of leukemic blasts in mice for therapeutic studies
Efficacy assessment	
Clinical and Bone Marrow Aspirate examinations and safety assessments are performed at baseline, at the End of induction cycles and if applicable at the end of each consolidation cycle. Disease status during maintenance will be evaluated at the end of each cycle and Follow-up after SCT every 3 months ± 28 days
 
If a patient discontinues treatment due to any other reason than disease progression/ death/ withdrawal of informed consent, the disease evaluations shall continue until definition of relapse-free survival are met. This includes patients who wish to discontinue treatment, but agree that further data is captured for the purpose of the study (partial withdrawal).

Safety assessment	All adverse events occurring during the course of the trial and for up to 30 days after the last dose of study medication will be captured, documented and reported. Toxicity will be graded twice weekly during treatment.

	
Until recovery of platelets and ANC, hematology assessments are done as often as necessary to determine the exact date of recovery of platelets and ANC.
 
Safety laboratory assessments include complete blood count, time to recovery of platelets $\geq 50 \times 10^9/L$ and $\geq 100 \times 10^9/L$, ANC recovery $\geq 0.5 \times 10^9/L$ and $\geq 1.0 \times 10^9/L$, clinical chemistry, including liver function test, coagulation, and 12-lead electrocardiogram as well as cardiac ultrasound.

Statistical considerations
	
Primary Efficacy Parameter The primary efficacy measure will be the rate of complete responders (CR).
 
Secondary Efficacy Parameters The secondary efficacy measures:
 
 • Rate of partial remissions • Percentage of patients being transplanted after induction therapy • Early death rate 
will be analyzed as rates.
 
 • Overall survival (OS); • Event-free survival (Events are defined as Death, not achieving a CR or CRi, Relapse after CR or CRi) 
will be described by median survival time and respective 95%-confidence intervals.


Sample size calculation
	
The sample size calculation is based on the evaluation of response rates according to Fleming for single-stage phase II designs. For the Fleming's procedure the two response levels p_0 (expected CR rate) and p_1 (meaningful increase in CR rate) are specified as $p_0=30\%$ and $p_1=60\%$:
 
$N=25$ patients should participate in the study to ensure a power of $1-\beta=0.90$ for the discrimination of p_0 and p_1. According to Fleming the null hypothesis should be rejected if at least
 $r = \left\lceil Np_0 + Z_{1-\alpha} \sqrt{Np_0(1-p_0)} \right\rceil + 1$ 
responses are observed ($\lceil x \rceil$ denotes the nearest integer to). With p_0 and N defined as above and $Z_{1-\alpha} = (1 - \alpha)$-quantile of the normal distribution = 1.645 at least 12 responders should be observed to show the efficacy as postulated.
 
Using the same approach in the 15 additional patients, submitted to an adapted drug regimen, the power will be 80% to discriminate a $p_0=30\%$ (expected CR rate) from a $p_1=65\%$ (meaningful increase in CR rate), if 8 out of 14 completed patients are considered as responders, with a one-tailed alpha error of 5%. Alternatively, the power will be 90% to discriminate a $p_0=30\%$ from a $p_1=70\%$ again if 8 out of 14 completed patients are considered as responders, with a one-tailed alpha error of 5%.

Accompanying baseline translational study (optional)	Leukemic blast cells will be isolated pre- and 24 hr post- a single Selinexor dose (60 mg) given at baseline (after registration and before first induction cycle). Blast cells will be used for leukemic stem cell gene expression profiling and in mouse model studies to define parameters associated with clinical responsiveness to Selinexor.
Data Monitoring Committee	An independent Data Monitoring Committee (DMC) will be implemented that reviews accumulating data of the clinical trial with respect to any potential safety issues, study progress and critical efficacy endpoints. The DMC will be an independent board consisting of 2-3 physicians with special expertise in AML. A physician is not allowed to participate in this clinical trial while serving on the DMC. The DMC will be supported by an independent statistician, if necessary. The DMC will review safety data, recovery times and efficacy of the clinical trial and support the interpretation of clinical trial results.

INFORMATION TO BE PROVIDED REGARDING SAES/PREGNANCY

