3.1.2 Definition of Treatment Cycle

All enrolled patients will be treated with cytosine arabinoside (Ara-C) at a dose of 100 mg/m² continuous infusion (day 1-7) and idarubicin at a dose of 10 mg/m² i.v. (days 1,3,5) every 4 weeks and Selinexor for a maximum of 2 cycles. During the second cycle the idarubicin dose is restricted to 2 administrations on day 1 and 3.

[figure not shown]
Patients will receive oral Selinexor 60 mg twice weekly in weeks 1-3 of a 4-week cycle (Monday/ Wednesday or Tuesday/ Thursday or Wednesday/Friday) starting on day 2 of week 1 (total of 6 doses per induction cycle).

If a CR or CRi was achieved, patients will be recommended for stem cell transplantation. If a PR is achieved patients can undergo a second, identical treatment cycle.

In patients who are not eligible or do not undergo additional stem cell transplantation, but, in the opinion of the investigator, are benefiting from Selinexor, then oral Selinexor dosed twice weekly in weeks 1-3 of a 4-week cycle may be continued parallel to 3 cycles of consolidation therapy with Ara-C until relapse or toxicity develops. The dose of Ara-C is 3 g/m² IV for 2h every 12 hours at 3 consecutive days for patients with good performance status and younger than 60 years (in total 6 doses). If patients are older than 60 years the dose is 1 g/m² IV for 2h every 12 hours at 3 consecutive days. During consolidation Selinexor dosing (60 mg) will start on day 2 of week 1 of a 4-week cycle and will be continued twice weekly during weeks 1-3 of a 4-week cycle (total of 6 doses per cycle). Selinexor twice weekly (Monday/ Wednesday or Tuesday/ Thursday or Wednesday/Friday) in weeks 1-3 at a dose of 60 mg (total of 6 doses per 4-week cycle) may continue until relapse or for maximally 1 year of treatment.

Patients achieving a > 50% blast reduction after the end of 2 induction cycles and in the opinion of the investigator, are benefiting from Selinexor and are not candidates for Stem cell transplantation, oral Selinexor dosed twice weekly in weeks 1-3 may be continued. Drug administration will occur twice weekly, on days 1 and 3 of weeks 1-3 of a 4-week cycle at a dose of 60 mg (e.g. on Monday and Wednesday or on Tuesday and Thursday or on Wednesday and Friday). One cycle is 4 weeks with 6 doses of Selinexor.

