3.1.3 Treatment Duration

Treatment duration for patients achieving CR or CRI during induction will be 1 or 2 cycles of 4 weeks each. These patients will be recommended for stem cell transplantation and have their end of treatment prior to SCT and will be followed for event-free and overall survival.

For patients achieving CR or CRI but who are not eligible or do not undergo additional stem cell transplantation, will continue in consolidation/maintenance therapy with 3 cycle of AraC combined with 4-week cycles with twice-weekly Selinexor during weeks 1 and 3 until relapse (for maximally 1 year of treatment).

Patients with a > 50% blast reduction at the end of 2 induction cycles and in the opinion of the investigator, are benefiting from Selinexor, will in maintenance therapy with 4-week cycles with twice-weekly Selinexor in weeks 1-3 until progression of disease (for maximally 1 year of treatment).

For patients for whom none of the above mentioned is achieved after 2 4-week induction cycles will discontinue study and will be followed for overall survival.

In any case, treatment will be discontinued upon progression of disease (PD) or unacceptable toxicity, withdrawal of consent by the patients, or non-compliance by the patient with protocol requirements.

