Asymptomatic Grade 3 or 4	
Delay Selinexor until \leq Grade 2, then restart at 1 dose level reduction (Table 2). Rule out other causes of amylase/lipase elevation. If levels have not returned to \leq Grade 2 within 3 weeks then no further Selinexor may be given and the patient should discontinue permanently from the study. A computed tomography (CT) scan or other imaging study to assess the pancreas, liver and gallbladder must be performed within 1 week of the first occurrence of any Grade 3 elevation of amylase and/or lipase.

Toxicity and Intensity	Dose Modification
Symptomatic Grade 3 or 4	Selinexor must be stopped immediately and proper supportive care provided. Evaluate enzyme levels at least twice weekly until resolution to ≤ Grade 1. Clinical manifestations should be monitored as needed until resolution or stabilization of the disease condition. Selinexor may be re-started at 2 dose levels below (Table 2) after resolution to ≤ Grade 1.
Pancreatitis (not observed to date)	
Grade 1	Maintain dose level
Grade 2, 3 or 4	Discontinue study treatment.
Thrombocytopenia	
Grade 1 or 2	Maintain dose. Rule out other causes including drug effects.
Grade 3 without bleeding	Rule out other causes including drug effects. For first occurrence: continue dosing without interruption: however, reduce Selinexor by 1 dose level. For ≥ second occurrence: interrupt selinexor and check platelet counts weekly until recovers to Grade 2 or baseline and reduce selinexor by 1 dose level. If the occurrence falls on a Day 1 of a cycle: delay start of cycle, check platelet counts weekly until recovers to Grade 2 or baseline and reduce selinexor by 1 dose level when resuming.
Grade 4 without bleeding	Rule out other causes including drug effects. Interrupt Selinexor until recovers to Grade 2 or baseline and reduce selinexor by 1 dose level. If the occurrence falls on a Day 1 of a cycle: delay start of cycle, check platelet counts weekly until recovers to Grade 2 or baseline and reduce selinexor by 1 dose level when resuming.

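### The maximum duration of Selinexor is stated inconsistently: no time limit in some places, one year in others, and no start date for the year

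*Protocol*

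**What the plan says.** Two groups can stay on Selinexor after induction: patients in CR or CRi who are not transplanted, and patients with more than 50% blast reduction after two cycles who are not transplant candidates. The Protocol describes how long in six places.

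- **Synopsis, study design row.** For the first group, Ara-C consolidation is given "in parallel to maintenance with Selinexor until relapse". Patients with more than 50% "blast reduction after 2 cycles will continue maintenance with Selinexor until PD". No time limit appears for either group.
- **Synopsis, treatment scheme row.** Both groups are limited to one year. For the blast-reduction group, "oral Selinexor dosed twice weekly may be continued until PD or for maximally 1 year of treatment".
- **The same row, general sentence near its end.** "Treatment will continue until progression of disease (PD) or unacceptable toxicity", with withdrawal of consent and non-compliance also listed. No time limit is mentioned.
- **Section 3.1.2.** The one-year limit is given for the consolidation group. For the blast-reduction group the text says only that "oral Selinexor dosed twice weekly in weeks 1-3 may be continued", with no end point.
- **Section 3.1.3, Treatment Duration.** Both groups are limited to one year. The blast-reduction group receives "twice-weekly Selinexor in weeks 1-3 until progression of disease (for maximally 1 year of treatment").
- **Section 5.4.** Reaching one year is not among the reasons for removal from treatment.

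Section 5.2.7 ties the primary analysis to the time when every patient is off study medication, 30 days after the last patient's last dose.

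**The concern.** A patient who reaches one year without progression or relapse is told to continue by one part of the Protocol and to stop by another. How long that patient is treated depends on which page the site follows.

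Three things depend on the stop date:

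- the exposure summary (SAP Section 11);
- the period in which adverse events are collected, which ends 30 days after the last dose (SAP Section 13.1);
- the date of the primary analysis (Protocol Section 5.2.7), which has no upper bound if dosing has none.

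The missing start date is a separate gap. Two sites that both apply the one-year limit could still stop at different times.

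**Working it through.** The plan gives no dose count to reproduce, so the check is a comparison of passages followed by simple arithmetic.

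**Comparison, for a patient free of progression or relapse at one year**

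| Place in Protocol | CR/CRi, not transplanted | More than 50% blast reduction |
|---|---|---|
| Synopsis, study design | until relapse, no limit | until PD, no limit |
| Synopsis, treatment scheme | at most 1 year | at most 1 year |
| Section 3.1.2 | at most 1 year | no end point given |
| Section 3.1.3 | at most 1 year | at most 1 year |
| Section 5.4 removal list | limit not named | limit not named |

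The study design row and Section 3.1.3 cannot both be followed for this patient.

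**Dose counts**

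Inputs: twice weekly in weeks 1 to 3 of a 4-week cycle (synopsis and Section 3.1.2); at most two induction cycles; one year taken as 52 weeks. The optional baseline dose is left out.

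- Doses per cycle: 2 × 3 = 6, which agrees with the Protocol.
- Year counted from first dose: 52 / 4 = 13 cycles; 13 × 6 = 78 doses.
- Year counted from maintenance after two induction cycles: 2 + 13 = 15 cycles; 15 × 6 = 90 doses. The unstated start date is therefore worth up to 90 − 78 = 12 doses, or 8 weeks.
- No limit: no ceiling follows from the text. As an extreme illustration, two years is 104 / 4 = 26 cycles; 26 × 6 = 156 doses.

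These are ceilings for a patient with no missed doses and no change of schedule.

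**Date of the primary analysis**

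Enrolment ended in June 2016 (Section 3.2), and treatment should start within two weeks of enrolment (Section 3.1). The last first dose is then about mid-July 2016, ignoring delays.

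- Year from first dose: about mid-July 2017, plus 30 days = about mid-August 2017.
- Year from maintenance after two cycles: 8 weeks later, about mid-October 2017.
- No limit: no date follows. End of study is two years after the last registration, about June 2018, but the text does not say that dosing stops then.

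**What does not move**

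- The SAP addendum (section 2) fixes the primary endpoint as best response after the induction cycle(s), before any maintenance.
- Patients in the blast-reduction group who did not reach CR or CRi cannot relapse from it. Under the Protocol, not achieving CR or CRi is already an event for event-free survival. Under SAP Section 12.2, event-free survival starts at CR/CRi. On either definition, the length of maintenance in this group changes neither measure.

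**The case against.** The strongest reply is that the limit is clear to anyone who reads the detailed text. Treating until progression and treating for at most one year are compatible, and Section 3.1.3 joins them in one sentence. That section is the one headed Treatment Duration, it covers both groups, and the synopsis treatment scheme agrees with it. On this view the study design row is a summary that left the limit out, and the silence in Section 3.1.2 is filled by the section that follows.

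Much of this stands. In particular, a reader might take the general sentence, "Treatment will continue until progression of disease (PD) or unacceptable toxicity", as a second instruction to treat without limit. It follows the limited text in the same row, and Section 3.1.3 places a parallel list directly after its own limit. It reads more naturally as the reasons for stopping early.

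Two things survive the reply. The study design row, read as written, directs treatment to continue and carries no limit. And no section, detailed or not, says when the year begins.

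The practical reach is also limited. Enrolment had closed before version 3.1 of January 2017. The SAP addendum of April 2018 shows that an initial analysis had already been run. No passage shows that sites differed, and none says how many patients reached one year. The 156-dose figure is therefore not an estimate of what happened.

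**Conclusion.** The duration point holds with moderate weight. It is an operative exposure rule, stated inconsistently, that also sets the date of the primary analysis. The gap between the two one-year readings is at most 12 doses (78 against 90). Against the unlimited reading the gap has no ceiling, and 156 doses over two years is an extreme illustration. The counts assume the current schedule, a 52-week year and two induction cycles.

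The point does not touch the CR/CRi rate after induction, nor time to relapse or event-free survival in the blast-reduction group. For CR/CRi patients who are not transplanted, an effect on relapse-based measures cannot be excluded, but the documents give nothing from which to size it.

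A reader might also infer a second contradiction, in Table 3 of Section 6.3.1. After symptomatic Grade 3 or 4 amylase or lipase elevation, "Selinexor may be re-started at 2 dose levels below (Table 2) after resolution to ≤ Grade 1", whereas under "Pancreatitis (not observed to date") Grades 2 to 4 lead to discontinuation. The documents do not support calling this a contradiction. The two rules stand under separate toxicity headings, and each is consistent in itself. What is missing is a stated boundary between them. Whether the rows overlap by grading definition cannot be checked, because Appendix 6 gives only its heading and not the CTCAE text.

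**What to change.** Reconcile the two synopsis rows (including the general sentence in the treatment scheme) and Sections 3.1.2, 3.1.3 and 5.4 to one statement of the maximum duration of Selinexor for each group, and state the day from which it is counted. The sponsor's clinicians decide the content.

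In the exposure table (SAP Table 14.3.1.1), flag every patient treated for more than one year. Count from first dose and from start of maintenance until the start date is settled. Section 6.2.3 already requires each dose and its date in the CRF, so no new data are needed.

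The same clarification could ask the sponsor's clinicians to state what separates the symptomatic amylase/lipase row from the pancreatitis row in Table 3.

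The cost is a wording change, by amendment or clarification letter, and one extra line in a planned table.
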